### **5.4. Additional analyses**

No other analyses than those specified above are planned.

### **5.5. Harms**

The safety data will be recorded and reported according to severity, expectedness, and causality. Only CTCAE grade 3-5 will be recorded. CTCAE grade 2 events will be recorded only for immune-related hepatotoxicity (increased hepatic enzymes).

The following events will be individually recorded and reported according to prevailing national procedures:

Pregnancy (including pregnancy occurring in a female partner of a male study participant), overdose, and SUSARs. The events will be analyzed on incidence case basis. Each site investigator is responsible for assuring that there are procedures and expertise available to cope with emergencies during the study.

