5.7.2.1 Dose delay criteria for IMP

Dose delay criteria apply for all drug-related AE. A treatment delay up to 4 weeks, *i.e.*, ≤6 weeks calculated from start of the previous therapy cycle, is allowed. A treatment delay beyond 6 weeks is not allowed ([Paragraph 5.7.2.3](#)).

Tumor assessments should continue as per protocol schedule, even if dosing is delayed.

Nivolumab administration will be delayed for the following reasons (in CTCAE grading):

- Any grade ≥2 non-skin drug-related AE, except for fatigue and laboratory abnormalities.
- Any grade 3 skin drug-related AE.
- Any grade 3 drug-related laboratory abnormality.
- Any AE, laboratory abnormality, intercurrent illness, or other reason which, in the judgment of Clinical Investigator, warrants delaying the dose of study medication.

Subjects who require delay of nivolumab will be re-evaluated weekly, or more frequently if clinically indicated. Nivolumab dosing can be resumed on the established dosing schedule when retreatment criteria are met ([Paragraph 5.7.2.2](#)).

FLOX administration will be delayed for the following reasons (in CTCAE grading):

- Grade 2 diarrhea (increase of 4–6 stools per day over baseline; moderate increase in stoma output compared to baseline; not interfering with ADL).
- Grade 3 diarrhea (increase of 7 or more stools per day over baseline; incontinence; severe increase in stoma output compared to baseline; interfering with ADL).
- Grade 2 myelosuppression (neutrophils of $1.0 \times 10^9/L$ to less than $1.5 \times 10^9/L$, or platelets of $50 \times 10^9/L$ to less than $75 \times 10^9/L$).
- Grade 3 myelosuppression (neutrophils of $0.5 \times 10^9/L$ to less than $1.0 \times 10^9/L$, or platelets of $25 \times 10^9/L$ to less than $50 \times 10^9/L$).
- Grade 4 myelosuppression (neutrophils less than $0.5 \times 10^9/L$, or platelets less than $25 \times 10^9/L$).
- Grade 2 sensory neuropathy (sensory alteration or paresthesia persisting between two oxaliplatin doses with no or only minor improvement, moderate symptoms, limiting instrumental ADL).

Subjects who require delay of FLOX will be re-evaluated weekly, or more frequently if clinically indicated. FLOX administration will be resumed when retreatment criteria are met ([Paragraph 5.7.2.2](#)).

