8.10 Reporting procedure

8.10.1 AE (adverse events) and SAE (serious adverse events)

All AE and SAE will be recorded in the patient's CRF.

SAE must be reported by Clinical Investigator to Sponsor by email and telephone to Principal Investigator, within 24 hours after the site has gained knowledge of the SAE (*c.f.*, Paragraph 8.2). Every SAE must be documented by Clinical Investigator on the SAE pages (to be found in Investigator Site File). The SAE report form must be completed, signed, and sent to Sponsor. The initial report shall promptly be followed by detailed, written reports if necessary. The initial and follow-up reports shall identify the trial subjects by unique code numbers assigned to the latter.

Sponsor will keep detailed records of all SAE reported by the investigators and performs an evaluation with respect to seriousness, causality, and expectedness.

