### 5. Analysis

#### 5.1. End point definitions

*Primary end point:* PFS; radiologic assessment every 8 weeks, according to the Response Evaluation Criteria in Solid Tumors (RECIST) and the RECIST consensus guideline for assessment of response to immune-modulating therapies, iRECIST.

*Secondary end points:*

Safety: incidence of adverse events (AE), as reported according to Common Terminology Criteria for Adverse Events (CTCAE) version 4.0 recorded on ongoing basis.

Tolerability: AE grading, as assessed by CTCAE v4.0 recorded on ongoing basis.

ORR: the percentage of patients with a confirmed complete response (CR) or partial response (PR).

DOR: the time from the first documentation of a CR or PR to disease progression.

SSCRR: the percentage of patients with a confirmed resection of metastatic disease with microscopically free margin (R0).

OS: the time from randomization to death of any cause.

QoL: assessment undertaken at study enrolment, completion of the active therapy of the first treatment sequence (after 16 weeks), and disease progression, using the consensus modules EORTC QLQ-C30, EORTC QLQ-CIPN20, and EQ-5D-5L.

*Tertiary end point:* Cost estimate; evaluation of the healthcare costs (relating to the sequencing procedures and administered medication) and health effects (quality-adjusted life years), expressed as incremental cost-effectiveness ratio, of the sequential therapy relative to the control group as comparator.

*Exploratory end points:* Various analyses will be undertaken for exploratory end points listed in 1.2.

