#### 5.2. Analysis methods

*Main statistical analyses.* The main statistical analysis is planned after the last patient has fulfilled the pre-defined follow-up period. PFS will be calculated from the day of randomization to first recorded disease progression according to RECIST v1.1 or when applicable iRECIST, or death. Patients who have not had disease progression at the time of final analysis will be censored at the date last known to be alive and progression-free. The analyses will compare the treatment groups in total as well as groups stratified by primary tumor sidedness and (K)RAS/BRAF mutation status.

*Interim analyses.* Interim analyses will apply to data on safety, tolerability, possible detrimental effects, and curative outcomes, and will be based on purely clinical judgment by the External Data and Safety Monitoring Committee. These types of data will be reported as the number of events.

*Descriptive statistics.* Demographic and clinical characteristics will be presented as means and standard deviations, medians with minimum and maximum values, or frequencies and percentages, as appropriate. Further statistical analyses will be separated to primary analyses, including only comparison of primary end point between two treatment arms, and secondary analyses, including stratified analyses on primary and secondary end points as well as number of analyses on secondary end points.

*Primary analysis.* Median PFS time will be compared between study arms by drawing Kaplan-Meier survival curves and performing log-rank test. HR with the corresponding 95% CI and p-values will be estimated by Cox proportional hazards model.

*Secondary analyses.* Distribution of PFS times stratified by the primary tumor sidedness and (K)RAS/BRAF mutation status will be illustrated graphically by Kaplan-Meier curves and compared by log-rank test. To assess the hazard rates for disease progression within each strata, Cox proportional hazards model will be estimated and, if appropriate, adjusted for relevant covariates. The results will be presented as HR with the corresponding 95% CI and p-values.

Safety. The number of serious adverse events (SAE) will be summarized and presented by trial arm. In addition, information will be given on the number of SAE per participant, together with details on the causality, expectedness, and outcome of each SAE experienced. Summaries of suspected unexpected serious adverse reaction (SUSAR) events will also be presented by trial arm.

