Tolerability. Summaries by trial arm will be produced to show the proportion of participants experiencing each grade of CTCAE toxicities overall and during each treatment cycle. For more detailed summaries, this information will also be broken down into the different types of toxicities.

QoL. This will be summarized for each treatment arm at study enrolment, completion of the active therapy of the first treatment sequence (after 16 weeks), and disease progression, using the consensus modules EORTC QLQ-C30, EORTC QLQ-CIPN20, and EQ-5D-5L. The data will be illustrated graphically and presented as mean scores with 95% CI at separate time points. The differences in QoL between two treatment arms throughout the study period will be assessed by estimating a linear mixed model with fixed effects for time and treatment arm and the interaction between these two. Random effects for patients will be included. A significant interaction will quantify differences between the groups and serve as an omnibus test.

Safety and tolerability in the treatment arms will be compared by  $\chi^2$  or Fisher's exact test, as appropriate.

ORR is defined as the percentage of patients with a confirmed CR or PR. The proportion of participants achieving at least PR will be summarized with corresponding 95% CI for each treatment arm. The difference between the trial arms in the proportion of participants achieving at least PR will also be presented with corresponding 95% CI. The difference between participants achieving at least PR and remaining participants will be assessed using logistic regression adjusting for treatment group and stratification factors. Odds ratios with corresponding 95% CI and p-values will be presented for all variables incorporated in the model.

SSCRR is defined as the percentage of patients with a confirmed resection of metastatic disease with microscopically free margin (R0). Corresponding analyses as those to be performed for ORR will be applied for SSCRR.

DOR is defined as the time from the first documentation of CR/iCR or PR/iPR to disease progression. DOR Kaplan-Meier curves will be drawn and compared by log-rank test. The median DOR with corresponding 95% CI will be presented by treatment group. Stratified analyses will be performed as well. The Cox proportional hazards model, adjusting for the stratification factors, will also be used to compare DOR

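### SAP 5.5 limits adverse event recording to CTCAE grade 3–5, which contradicts the SAP's own safety and tolerability endpoints and the protocol's rule that all adverse events enter the CRF

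*SAP*

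**What the plan says.** SAP 5.5 (Harms) sets the recording rule: "Only CTCAE grade 3-5 will be recorded". Its next sentence makes one exception: "CTCAE grade 2 events will be recorded only for immune-related hepatotoxicity (increased hepatic enzymes").

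SAP 5.1 defines the two secondary endpoints concerned without a grade threshold: "Safety: incidence of adverse events (AE), as reported according to Common Terminology Criteria for Adverse Events (CTCAE) version 4.0 recorded on ongoing basis" and "Tolerability: AE grading, as assessed by CTCAE v4.0 recorded on ongoing basis". For tolerability, SAP 5.2 plans summaries by arm of "the proportion of participants experiencing each grade of CTCAE toxicities overall and during each treatment cycle", and protocol 10.4.5 plans the same. Both documents compare safety and tolerability between arms by a chi-square or Fisher's exact test and name no grade cut-off. The Safety paragraph of SAP 5.2 is narrower than the endpoint definition: "The number of serious adverse events (SAE) will be summarized and presented by trial arm", followed by SAE per participant and SUSAR summaries.

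The protocol's recording rule is the reverse of SAP 5.5. Protocol 8.10.1 says "All AE and SAE will be recorded in the" CRF of the patient. Protocol 8.1.1 classes FLOX events of grade 2 or lower as non-serious, exempts non-serious events from reporting, and still has them entered on a dedicated CRF page.

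**The concern.** Safety and tolerability are among the outcomes on which both documents say superiority will be investigated (protocol section 3, SAP 2.1). A rule that drops grade 1 and nearly all of grade 2 removes the part of the toxicity profile that matters most for tolerability in this design:

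- Protocol 5.7.2.1 makes grade 2 events a trigger for delay. This covers most non-skin nivolumab-related events, and diarrhea, myelosuppression and sensory neuropathy on FLOX.
- Protocol 5.7.2.3 ends FLOX at grade 3 sensory neuropathy, so grade 2 is the last grade before discontinuation.
- Protocol 4.6 raises the possibility that sequential nivolumab dampens the side effects of FLOX. A benefit confined to grades 1–2 would not show in adverse event data recorded under SAP 5.5.

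There is also a risk in reporting. An incidence of adverse events could be published under the SAP 5.1 definition when it contains only grade 3–5 events and one kind of grade 2 event.

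**Working it through.** The plan gives no figure on this point to reproduce. The check sets the recording rules against the planned outputs.

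**Step 1: what each rule captures**

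| Rule | Grade 1 | Grade 2 | Grades 3–5 |
|---|---|---|---|
| Protocol 8.1.1, 8.10.1 | recorded | recorded | recorded |
| SAP 5.5 | not recorded | immune-related hepatotoxicity only | recorded |

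**Step 2: what each planned output needs**

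| Output | Source | If the protocol rule was followed | If SAP 5.5 was followed |
|---|---|---|---|
| Incidence of any adverse event | SAP 5.1 | available | reduces to grade 3–5 plus grade 2 immune-related hepatotoxicity |
| Proportion at each grade, overall and per cycle | SAP 5.2, protocol 10.4.5 | 5 of 5 rows | 3 of 5 rows complete, grade 1 empty, grade 2 one event type |
| Between-arm test of grade 3–5 toxicity | SAP 5.2, protocol 10.4.5 | available | available |
| SAE and SUSAR summaries | SAP 5.2, protocol 10.4.5 | available | available |
| PFS | SAP 5.2 | unaffected | unaffected |

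The SAE row holds because protocol 8.9 separates seriousness from severity and protocol 8.2 requires every SAE to be collected, whatever its grade.

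**Step 3: recording or reporting?** SAP 5.5 opens by using both verbs, for data that are recorded and reported. It then applies only the verb for recording to the restriction, and again to the exception. Protocol 8.1.1 draws the same distinction and waives only reporting for low grades. Where the plan wants grade 3–5 for a particular purpose, as in the interim counts of protocol 10.4.2 and SAP 2.5, it says so at that place. As worded, SAP 5.5 is therefore a recording rule.

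**Step 4: balance between arms.** The grade 2 exception applies to immune-related hepatotoxicity, not to every rise in liver enzymes. A grade 2 rise attributed to FLOX would go unrecorded, while one attributed to nivolumab would be recorded. Nivolumab is planned only in the experimental arm, and the trial is open-label. The exception would thus probably add grade 2 events mainly to that arm. The documents give no rate from which to size this.

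**Step 5: illustration under assumed rates.** Let p_any be the proportion of patients with any adverse event and p_3–5 the proportion with a grade 3–5 event. Ignoring the hepatotoxicity exception, the share of patients with an adverse event who would appear to have none is 1 − p_3–5 / p_any. The documents give neither rate. Assuming p_any = 0.95:

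- p_3–5 = 0.30: 1 − 0.30/0.95 = 0.68
- p_3–5 = 0.50: 1 − 0.50/0.95 = 0.47
- p_3–5 = 0.70: 1 − 0.70/0.95 = 0.26

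These figures show only that any-event incidence and grade 3–5 incidence can be far apart.

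**The case against.** The strongest reply is that nothing need be missing. The protocol requires all adverse events in the CRF. If sites followed it, grades 1–2 are in the database and SAP 5.5 is at most a badly worded reporting limit. The Safety paragraph of SAP 5.2 counts SAE and SUSAR, which do not depend on grade, and grade 3–5 toxicity can still be compared between arms. Neuropathy has a second source in the EORTC QLQ-CIPN20, which is compared between arms by a mixed model. These are secondary endpoints in a phase 2 trial, and the primary analysis and sample size do not depend on them.

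Most of this stands. A reader might infer that the safety and tolerability endpoints cannot be computed, or that no comparison of tolerability is possible. The documents do not support either inference. The first presumes that SAP 5.5 governed capture, which neither document establishes, and the second overlooks the grade 3–5 and SAE comparisons.

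The reply does not remove the contradiction. The per-grade, per-cycle table is a promised output in both documents and needs grades that SAP 5.5 says will not be recorded. The QLQ-CIPN20 is collected at three time points, does not give CTCAE grades and covers no other toxicity. SAP 5.3 expects few missing values and plans no handling for them, so it does not address events left out by rule.

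**Conclusion.** SAP 5.5 is wrong as written. It conflicts with SAP 5.1 and 5.2 and with protocol 8.1.1, 8.10.1 and 10.4.5. That conclusion rests on the texts alone.

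The consequence is conditional. If SAP 5.5 governed data capture, two of the five grade rows could not be produced as planned, any-event incidence would not match its definition, and the single grade 2 exception would probably act mainly in the nivolumab arm. If the protocol governed, the data exist and the defect is one of wording. The documents do not show which rule the sites followed. The last part of the conditional finding also assumes that events judged immune-related arise chiefly where nivolumab is given.

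**What to change.** First establish from the CRF whether grades 1–2 were entered.

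- **If they were, or recording can still follow the protocol:** delete the grade restriction in SAP 5.5, state that all grades are recorded as in protocol 8.1.1 and 8.10.1, and report by grade. The cost is SAP wording.
- **If they were not:** restate the safety and tolerability endpoints and tables in SAP 5.1 and 5.2 as grade 3–5 plus SAE. Apply one capture rule to both arms, show grade 2 hepatotoxicity separately, and do not call the result the incidence of all adverse events. The cost is that both stated endpoints become narrower, and low-grade events that were never captured may not be recoverable.

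Replacing the lost grades with dose delays and reductions as the tolerability measure is not recommended. Neither document defines that endpoint, and SAP 5.4 plans no further analyses. Protocol 10.4.1 allows changes to the statistical plan until the day of database lock, and requires deviations from the original plan to be described and justified in the clinical study report.

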### **5.6. Statistical software**

SPSS Statistics, SAS, STATA, and GraphPad Prism (the most recent versions for all) are relevant software for statistical analyses of the study data.

